4.4 STRATEGIES FOR RECRUITMENT AND RETENTION

- *We will enroll up to 8 participants per month depending on the time within the study.*
- *Study team will call participants monthly to maintain contact and obtain interim history regarding development of new DFU.*

5 INFORMED CONSENT PROCESS

- The study team will obtain informed consent in the study clinic (CTSA)
- There will be no waiver to obtaining signed informed consent
- This study is limited to adults
- Costs of transport from study clinic will be \$60 (enrollment only)

- during clinic visit, the study will be explained, history (see Case Report Form) taken, and an examination of both feet will be recorded. No other tests will be performed
- There are no costs incurred by the study subject.
- Participant Recruitment is as described, patients with a history of DFU, will be recruited: inclusion and exclusion criteria are noted in section 4.0
- Risk/Benefit: Study subjects may or may not receive personal, direct benefit from taking part in this study. The possible benefits of taking part in this study include identification of early signs of diabetic foot ulcer that we can manage to prevent ulcers.
- Data quality control and database management: all data will be maintained in a password protected database: MONTEBOX. Only IRB approved study team members will have access.

6 STATISTICAL CONSIDERATIONS

This study is primary to assess adherence to the monitoring device. It is not powered to assess clinical outcomes or use of health care resources.

- We will plan for 20 subjects to complete the study, and plan to enroll up to 40 patients to account for drop out or exclusion.
- Measurement of adherence (primary outcome)
 - Adherence is defined as > 3 days/week during the six month period
 - We will record the number of re-engagement calls per participant over the 6 month study period
 - We will record the number lost to follow up, unable to comply, or are hospitalized (4.2, 4.3)
- Measurement of secondary outcomes
 - Number of subjects who develop a DFU over the course of the study
 - Utilization of health care resource use (total number of: ER visits, outpatient visits) over the course of the study

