4.3 A STUDY SUBJECT DEVELOPS A DFU REQUIRING HOSPITALIZATION

1. Data is censored from the date of hospital admission.

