7 STUDY INTERVENTION DISCONTINUATION AND PARTICIPANT DISCONTINUATION/WITHDRAWAL

7.1 DISCONTINUATION OF STUDY

Participant discontinuation would occur if the participant were unable or unwilling to continue in the study.

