7.2 PARTICIPANT DISCONTINUATION/WITHDRAWAL OR LOSS TO FOLLOW UP

Participants are free to withdraw from participation in the study at any time upon request.

An investigator may discontinue or withdraw a participant from the study for the following reasons:

- Significant non-compliance
- If any clinical adverse event (AE), laboratory abnormality, or other medical condition or situation occurs such that continued participation in the study would not be in the best interest of the participant.

- If the participant meets an exclusion criterion (either newly developed or not previously recognized) that precludes further study participation
- Loss to follow up will be if he or she cannot be reached by the study staff.

The reason for participant discontinuation or withdrawal from the study will be recorded on the Case Report Form (CRF). In the event a participant withdraws from the study or is lost to follow up, we will enroll an additional participant.

Figure 5. Image of foot monitoring device

References

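### The primary adherence denominator is undefined, and the completer target, replacement rule and withdrawal for non-compliance lead toward a completers-based estimate that is likely biased upward

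*Combined protocol and SAP*

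**What the plan says.** The only sample-size statement is in Section 6: "We will plan for 20 subjects to complete the study, and plan to enroll up to 40 patients to account for drop out or exclusion". The same section gives the primary outcome: "Adherence is defined as > 3 days/week during the six month period". Under that outcome it also lists a count of participants who are lost, cannot comply or are hospitalised, with a cross-reference to Sections 4.2 and 4.3. It does not say how any of them enter the adherence result.

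The rules for leaving the study are in Sections 4.3, 7.1 and 7.2:

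- Section 7.1: "Participant discontinuation would occur if the participant were unable or unwilling to continue in the study".
- Section 7.2 lists "Significant non-compliance" among the reasons for which an investigator may withdraw a participant. A newly met exclusion criterion is another, and Section 4.2 makes inability to comply with study requirements an exclusion criterion.
- Section 7.2 on replacement: "In the event a participant withdraws from the study or is lost to follow up, we will enroll an additional participant".
- Section 4.3, for a foot ulcer that needs hospital admission: "Data is censored from the date of hospital admission".

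Section 1.2, part C (Intervention), also tells participants to stop using the mat in certain clinical situations, such as a new ulcer or an offloading device. How those days count toward adherence is not stated.

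**The concern.** The study asks whether patients keep using the mat. A participant who loses interest, cannot be reached or is withdrawn for not using it has supplied an answer to that question, and usually an unfavourable one. In a trial of another outcome such a person might be missing data; here the exit is largely the outcome itself.

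Three features of the plan work in the same direction. The target is counted in completers. Each withdrawal or loss brings in another participant. Poor use can itself be a ground for removal, either directly or by treating the person as newly excluded under Section 4.2. With no stated denominator, the natural analysis is the adherence rate among the 20 who finish, and that selects participants on the outcome. The denominator could also be chosen after the data are seen.

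Sections 2.1 and 3.1 say the study is meant to show uptake and adherence in this population and to inform larger trials. A rate that describes only those who stayed would be read there as the rate for everyone offered the mat.

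**Working it through.** **1. The plan's own figures.** Section 6 gives 20 completers and a ceiling of 40. Inflating for loss, N = 20/(1 − d):

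- d = 20%: 20/0.8 = 25
- d = 33%: 20/0.667 = 30
- d = 50%: 20/0.5 = 40

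The ceiling is matched only at 50% loss. The documents state no loss rate, so this value is solved backwards from the 40 and does not confirm it. The 20 has no target rate, precision or power behind it and cannot be reproduced.

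**2. Assumptions for the illustration.** The documents give no adherence rate, so 16 adherent among 20 completers is assumed. Each participant is treated as simply adherent or not over the six months. N is the number given a mat, taken as 25, 30 or 40. Let q be the share of non-completers who are non-adherent.

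**3. Formula.** Rate among all given a mat = [16 + (1 − q)(N − 20)]/N.

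Completers only: 16/20 = 80.0%, exact (Clopper-Pearson) 95% CI 56.3% to 94.3%.

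| N given a mat | q = 1 (exact 95% CI) | Gap from 80% | q = 0.5 | Gap from 80% |
|---|---|---|---|---|
| 25 | 16/25 = 64.0% (42.5 to 82.0) | 16 points | 18.5/25 = 74% | 6 points |
| 30 | 16/30 = 53.3% (34.3 to 71.7) | 27 points | 21/30 = 70% | 10 points |
| 40 | 16/40 = 40.0% (24.9 to 56.7) | 40 points | 26/40 = 65% | 15 points |

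**4. Direction.** The gap equals [(N − 20)/N] × (0.80 − (1 − q)). It is zero when q = 0.20, that is, when non-completers are as adherent as completers. It is positive for any larger q. At q = 0 it reverses: the rates become 84%, 87% and 90% for N = 25, 30 and 40. The upward direction therefore rests on non-completers being less adherent than completers. That is likely when unwillingness and non-compliance are reasons for leaving, but it is not certain.

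**5. The extreme.** With q = 1 the completer rate is overstated by the factor N/20: 1.25, 1.5 or 2.0. At the ceiling, even 20 adherent out of 20 completers would be 20/40 = 50% (33.8% to 66.2%) of those given a mat.

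**6. Against sampling error.** The q = 1 results for N = 30 and N = 40 (53.3% and 40.0%) fall below the whole completer interval of 56.3% to 94.3%. The other results in the table lie inside it, so under milder assumptions the bias is smaller than the sampling uncertainty.

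**The case against.** A reader might infer that the plan commits itself to a completers-only result, so that those who stop are dropped from the denominator. The documents do not say so. Twenty completers is a planning target, and the analysis set is simply not defined. The counts of those lost, unable to comply or hospitalised are listed under the primary outcome, and Section 7.2 records the reason for each exit, so an analysis of everyone remains possible.

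Replacement is also easy to over-read. Section 7.2 adds a participant; it does not say that the one who left is removed from analysis. Adding people causes no bias if everyone stays in. Replacement is limited by the ceiling of 40, and no replacement is stated for participants censored at hospital admission.

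The 40-point gap is a worst case. The ceiling covers exclusions as well as dropout, and Section 1.2, part B (Enrollment), lists consent before the review of eligibility, so some of the 40 may never receive a mat. Some exits are medical and some non-use is instructed; neither is a choice to stop.

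Finally, a reader might infer from Section 4.4 ("We will enroll up to 8 participants per month depending on the time within the study") that replacements could not finish in time. That figure is a maximum, not a rate, and timing says nothing about bias in the estimate.

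All of this limits the claim to an undefined denominator, with rules that favour a selected one. It does not remove the gap: recording the counts makes a sound analysis possible but does not commit anyone to it.

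**Conclusion.** The concern holds as a defect of specification. The sole primary outcome has no stated denominator and no rule for scoring early stoppers. The completer target, the replacement rule and withdrawal for non-compliance lead toward an estimate selected on the outcome, and such an estimate is likely biased upward.

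On an assumed 16 adherent among 20 completers, the overstatement is about 6 to 40 percentage points. The low end is 25 given a mat with half the non-completers non-adherent; the high end is 40 given a mat with all of them non-adherent. These figures illustrate the range and do not predict the result. The documents supply neither an adherence rate nor a loss rate, and the bias disappears if non-completers use the mat as well as completers do. The need to fix the denominator before the data are seen does not depend on where in that range the truth lies.

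**What to change.** In Section 6:

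- Define the primary analysis set as every eligible consented participant given a mat, including those who never complete activation.
- Count as non-adherent all weeks after voluntary withdrawal, loss to follow-up or investigator withdrawal for non-compliance, and all weeks of uninstructed non-use.
- Give a separate prespecified rule for weeks of instructed non-use (Section 1.2, part C) and for time censored at hospital admission (Section 4.3). These are not voluntary non-adherence. One option is to remove those weeks from the participant's own denominator, with a sensitivity analysis that treats them differently.
- Report the completer figure only as a labelled supportive analysis.

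In Section 7.2, keep the replacement sentence if wanted, but state that additional participants are added to the denominator and that those who left stay in it.

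The change is one of wording in two sections, with no extra participants or data. Its downside is that the reported adherence will be less favourable.

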7 STUDY INTERVENTION DISCONTINUATION AND PARTICIPANT DISCONTINUATION/WITHDRAWAL

7.1 DISCONTINUATION OF STUDY

Participant discontinuation would occur if the participant were unable or unwilling to continue in the study.

7.2 PARTICIPANT DISCONTINUATION/WITHDRAWAL OR LOSS TO FOLLOW UP

Participants are free to withdraw from participation in the study at any time upon request.

An investigator may discontinue or withdraw a participant from the study for the following reasons:

- Significant non-compliance
- If any clinical adverse event (AE), laboratory abnormality, or other medical condition or situation occurs such that continued participation in the study would not be in the best interest of the participant.

- If the participant meets an exclusion criterion (either newly developed or not previously recognized) that precludes further study participation
- Loss to follow up will be if he or she cannot be reached by the study staff.

The reason for participant discontinuation or withdrawal from the study will be recorded on the Case Report Form (CRF). In the event a participant withdraws from the study or is lost to follow up, we will enroll an additional participant.

Figure 5. Image of foot monitoring device

References

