1.2 SCHEMA

A. Overall study design

1. *Subjects will be identified from the EMR: Adults that were treated for DFU within past 24 months, who presently have no active DFU at the time of study consent.*
2. *Consent and enrollment: we will approach patients via email if available, and/or phone call/phone text to learn about the study. Subjects can also be enrolled during routine clinic visit by study member.*
3. *Interested patients will be seen in the CTSA study clinic or enrolled in their care clinic (primary care, vascular, podiatry etc), if they fulfill criteria we will obtain informed consent.*
4. *For consented patients: baseline demographic data will be extracted from the EMR and case report filled out.*
5. *All study subjects receive the intervention and training from Podimetrics.*
6. *Study subjects will be instructed how to set up the mat and directed to step on the mat daily*
7. *If they do not step on the mat, they will be contacted by Podimetrics to reinforce use*

8. Increase in foot temperature (increase in 2.2°C over two consecutive uses between and of six contralaterally sites), a marker for early ulcer, will trigger a call to the study team to the study subject and the PI for management (SOP of elevated temperature management below).
9. All study subjects will be called each month to determine if any ulcer development or health care utilization.

[figure not shown]
[figure not shown]

Figure 1. Overall study protocol

B. Enrollment

1. Potential study subjects will be contacted by email, if no response will follow up with phone call. If by email they are interested to hear more about the study we will then follow up with description of study. Patients will also be recruited from outpatient clinics (podiatry, primary care, vascular, endocrine) by study team members.
2. For patients who are interested in the study we will obtain consent in a study clinic visit

(they will get reimbursed for travel to study clinic).

3. Study clinic: obtain informed consent, obtain history, examine feet, review enrollment criteria,

Figure 2. Enrollment protocol

[figure not shown]
C. Intervention

1. After informed consent at study clinic, we will provide the mat and standardized training (45 minutes by phone preferably within one week of receiving mat-this is the Activation or on boarding). Subjects step on mat daily and Podimetrics will receive and interpret daily data generated by the mat. A prescription for the Mat will be faxed to Podimetrics.

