4.2 EXCLUSION CRITERIA

1. Active DFU
2. Unable to comply with study requirements.
3. Prior AKA or BKA

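### Section 7.2 allows withdrawal for undefined non-compliance in a study whose primary outcome is compliance with the mat, and no denominator rule protects the adherence estimate

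*Combined protocol and SAP*

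**What the plan says.** Section 6 sets the purpose: "This study is primary to assess adherence to the monitoring device". The outcome is then given as "Adherence is defined as > 3 days/week during the six month period". The Schema (1.2) makes mat use the main thing asked of participants, who are "directed to step on the mat daily".

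Section 7.2 gives the withdrawal power: "An investigator may discontinue or withdraw a participant from the study for the following reasons". The first reason listed is "Significant non-compliance". A later one reads "If the participant meets an exclusion criterion (either newly developed or not previously recognized) that precludes further study participation". Among the exclusions in 4.2 is "Unable to comply with study requirements".

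Three other provisions bear on the point:

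- Section 7.2 provides for an additional participant when one withdraws or is lost, and for the reason to be entered on the case report form.
- Section 6 plans for 20 participants to finish and up to 40 to be enrolled, the margin being for drop-out or exclusion.
- Section 6, under the measurement of adherence, calls for a count of those lost, unable to comply or hospitalized, with a cross-reference to 4.2 and 4.3.

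No section defines the analysis population or says how a participant withdrawn for non-compliance is scored.

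**The concern.** In most trials a non-compliance clause is routine. Here compliance with the mat is the endpoint. A participant who rarely steps on the mat is an outcome event, and the same behaviour can be grounds for ending that person's participation. Replacement, and a target counted in completers, then favour a final sample richer in users than the group that started.

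Two things are at stake. The first is the adherence proportion, which would be too high if it were computed on those who remain. The second does not depend on the denominator. Withdrawal ends observation, so six-month adherence, later response to re-engagement calls, and ulcer and utilization data from the monthly calls are lost for non-users. They are the participants from whom a study of uptake has most to learn, and Section 3.1 says the results are to inform larger trials.

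**Working it through.** **1. The plan's own figure.** Section 6 gives 20 completers and up to 40 enrolled, with no drop-out rate. With N/(1 − d) and N = 20, rounding up:

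| d | 10% | 20% | 30% | 40% | 50% |
|---|---|---|---|---|---|
| Enrolled | 23 | 25 | 29 | 34 | 40 |

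The ceiling of 40 matches d = 50%. That rate is back-calculated, not stated. It shows how much loss and replacement the plan can absorb.

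**2. Does the withdrawal rule reach the outcome?** Daily mat use is a study procedure (Schema). Section 7.2 sets no threshold for non-compliance and does not limit it to other procedures, so low mat use falls within it. The second route works as follows: 7.2 covers exclusions that develop after enrolment, and exclusion 2 in 4.2 is inability to comply. Nothing elsewhere in the document blocks either route.

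**3. Effect if withdrawn participants leave the denominator.** Let a be true adherence among starters and f the share of the non-adherent who are withdrawn. Both are assumptions, since the documents give no expected rate. Then

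observed = a / [a + (1 − a)(1 − f)]

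| a | f | Calculation | Observed |
|---|---|---|---|
| 60% | 50% | 0.60/(0.60 + 0.20) | 75% |
| 60% | 75% | 0.60/(0.60 + 0.10) | 86% |
| 50% | 50% | 0.50/(0.50 + 0.25) | 67% |
| 50% | 75% | 0.50/(0.50 + 0.125) | 80% |

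The first row in whole participants: 25 start, 15 adherent and 10 not. Five of the 10 are withdrawn, leaving 20 completers. Completers give 15/20 = 75%; all starters give 15/25 = 60%. This fits within the ceiling of 40. If the five are counted as non-adherent, the inflation is zero.

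**4. Effect at the planned size.** Assume 16 of 20 completers are adherent and w further participants were withdrawn for mat non-use and replaced. The completers figure is 16/20 = 80% (exact 95% CI 56–94%) whatever w is. Over all enrolled:

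| w | 5 | 10 | 15 | 20 |
|---|---|---|---|---|
| Adherent/enrolled | 16/25 | 16/30 | 16/35 | 16/40 |
| Proportion | 64% | 53% | 46% | 40% |

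At w = 20 the exact 95% CI is 25–57%. Since 40/20 = 2, the completers figure can be at most twice the all-enrolled figure.

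**The case against.** The case on the other side has weight.

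- **Withdrawal from follow-up is not removal from analysis.** A reader might infer that the plan drops non-users from the estimate. It does not say so; it neither requires nor forbids a completers analysis. The inflation is therefore conditional.
- **Non-compliance is not the same as low mat use.** The term could also cover missed monthly calls or other procedures. It overlaps with the outcome without being identical to it.
- **Safeguards exist.** The power is discretionary, reasons and counts are recorded, and the stated response to missed use is reinforcement. These make withdrawals visible, but they set no denominator and do not restore lost follow-up.
- **Section 6 might seem to set inability to comply apart from adherence.** It does not: the count is listed under the measurement of adherence. The reference to 4.2 leaves unclear whether that exclusion is applied after enrolment.
- **A reader might suppose that the study team watches usage as it accrues.** The document does not establish this. The device company receives the data and handles missed use; the team is described as reviewing data after a temperature elevation. The point does not need it.
- **The replacement sentence does not name investigator withdrawals explicitly.** Including them is a natural reading, not a certain one.

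What remains is an undefined discretion that reaches the primary outcome, with nothing in the analysis section to neutralise it.

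**Conclusion.** The point holds in a conditional form. The rules allow selection on the primary outcome and cost follow-up on non-users; they do not by themselves show that the estimate will be biased. The size runs from no inflation, if those withdrawn for mat non-use are counted as non-adherent, to a doubling, if 20 of 40 are withdrawn for that reason and only completers are analysed. Intermediate cases, such as 60% appearing as 75%, rest on assumed adherence and withdrawal rates and on dropping the withdrawn from the denominator. The lost follow-up arises under any denominator. This is more than missing detail, because a written rule acts on the only primary outcome. The stronger reading, that non-users will be removed and adherence overstated, is not supported.

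**What to change.** - **Section 7.2:** state that mat non-use alone is not a reason for withdrawal, and that such participants continue the planned monthly calls to month 6. The reason concerning adverse events and other medical conditions is unaffected.
- **Section 4.2:** state that exclusion 2 applies at screening only.
- **Section 6:** state that the primary analysis includes all enrolled participants (or all who completed activation; choose one in advance). Anyone withdrawn or lost for mat non-use counts as non-adherent. Completers are reported only as a supportive analysis.
- **Protocol-directed interruptions:** say how time is handled when the Schema (part C, item 3) tells participants to stop using the mat, or when 4.3 censors data at hospital admission. Keep this separate from non-adherence. Scoring all low or zero use as non-adherent would penalise participants for following the protocol and bias the estimate downward.

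The cost is a few sentences. Mats stay longer with non-users, and the reported adherence may be lower. The monthly calls are already planned.

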1 PROTOCOL SUMMARY

1.1 SYNOPSIS

Title: Adherence to novel foot mat technology for early detection of DFU.

Study Description:

Innovations toward the prevention of DFU are needed. Early detection of changes in the foot that predict the development of DFU could allow timely intervention to prevent the limb damage that occurs with advanced DFU.

Studies have demonstrated that increased temperature in the foot presage the development of DFU. Temperature changes can accurately be detected by home monitoring devices and predict impending ulceration. Here we will test the uptake of novel foot temperature monitoring technology for a future intervention study to determine if a home monitoring device could prevent the occurrence of severe DFU for our patients at MMC.

We will conduct a longitudinal study to determine the adherence to an FDA cleared device, Podimetrics, which has been tested in other populations and shown to 1) decrease the risk of severe DFU, and 2) decrease the utilization of health care resources in high risk patients with a history of DFU. For this study, we will identify and enroll patients who are high risk for DFU. They will be identified from the EMR. After informed consent, study subjects will receive the foot mat and obtain training remotely from Podimetrics, which provides a standardized training program. Study subjects briefly stand on the mat daily, and the temperature data automatically is sent for analysis to Podimetrics to interpret the information. The study subjects will be evaluated over a six-month period to measure their daily use of the technology. Secondary outcomes of this study include the occurrence of DFU and use of health care resources. Study subjects will be contacted every month by the study team to assess foot health. Study subjects will be instructed to contact the study team during the study period to inquire if they develop any changes in the foot such as the diagnosis of DFU or require a foot cast for offloading or have any concerns about their feet.

If patients have an increase in temperature, the study team will be contacted by Podimetrics. After a review of symptoms, a standard care protocol will be executed: offloading (decrease in weight bearing) will be recommended. In one study 68% of cases

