The mechanism of the development of neuropathic foot ulcerations involves repetitive trauma at pressure point on the sole of the foot over several days. Due to the neuropathy, patients do not detect subtle inflammatory changes in the foot such as pain, erythema, swelling which are harbingers of ulceration. It has been shown that an increase in foot temperature as defined as increase by 2.2°C or 4°F, can detect early inflammatory changes, and if offloading is instituted, healing can occur to prevent ulceration. We will test the feasibility of a home foot temperature monitoring system in our MMC patients with Type 1 or Type 2 diabetes. Study subjects will stand on the mat daily, the temperatures are transmitted and if there are significant changes, the provider is alerted. There is a growing literature that demonstrating that these devices allow prompt detection and treatment to prevent severe DFU and need for a lower extremity amputation (LEA). Using FDA approved technology from Podometrics (Somerville, Massachusetts), study subjects can use a telemedicine foot temperature monitoring mat to monitor the bottoms of their feet daily. This requires them to step on the mat, and the data will be automatically transmitted to Podometrics for analysis. The mat embeds cellular technology for the transmission to occur. The use of this device has shown to (1) reduce the rate of hospitalization (RRR 0.52), (2) lower extremity amputation (RRR 0.71), (3) reduce the number of outpatient visits and (4) reduce the development of severe wounds (RRR 0.91). Podometrics is an FDA 510 (k) cleared medical device for evaluation of the temperature over the soles of the feet for signs of inflammation.

Podometrics provides the mat, wireless transmission of data, patient/subject training in the use of the mat, and reinforcement in the case of non-adherence. The Podometrics team monitors the data and when there is an increase in 2.2°C over two consecutive uses between and of six contralaterally matched locations, the study team is contacted. Accuracy of this approach predicts 97% of plantar DFU in patient in diabetic foot remission.

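### Loss to follow-up is defined by staff contact and leads to replacement, while the primary outcome arrives without contact and no rule keeps lost participants in the adherence denominator

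*Combined protocol and SAP*

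**What the plan says.** Section 7.2 gives the definition of loss in one sentence: "Loss to follow up will be if he or she cannot be reached by the study staff". It sets no number of attempts, no time window and no check of whether the mat is still transmitting. The consequence follows in the same section: "In the event a participant withdraws from the study or is lost to follow up, we will enroll an additional participant".

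Section 6 defines the primary outcome: "Adherence is defined as > 3 days/week during the six month period". It aims for 20 completers and allows enrolment of up to 40 to cover drop-out or exclusion. It says that the number lost will be recorded, but gives no rule for analysing their mat data.

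The primary data arrive without staff contact. The Synopsis (1.1) says "the temperature data automatically is sent for analysis to Podimetrics to interpret the information", and Section 2.2 adds "The mat embeds cellular technology for the transmission to occur".

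Staff contact serves other purposes. Section 1.2 says "All study subjects will be called each month to determine if any ulcer development or health care utilization", and Section 4.4 describes the same monthly call. The process for temperature elevations in Section 1.2 D also depends on speaking to the participant.

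Two other provisions bear on the data. Section 4.3 censors data from the date of admission when a foot ulcer leads to hospitalization. Section 1.2 C lists circumstances in which participants are told to stop using the mat.

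**The concern.** The loss criterion fits the outcomes collected by telephone, but it is applied to the whole study. Adherence can still be observed in someone who does not answer the phone, because the mat reports use by itself. If that person is declared lost, an additional participant is enrolled, and the study works toward a target counted in completers.

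Adherence is the one result that this study is designed to deliver, and Section 3.1 says that the data are to inform larger trials. If the reported proportion covers only those who completed, it answers a different question from the proportion of all enrolled participants who used the mat. The two can differ whenever being reachable is related to using the device.

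**Working it through.** **1. What the rules allow.** Loss depends only on contact, and loss leads to replacement (Section 7.2). The primary outcome depends only on mat use, which is transmitted automatically (Sections 1.1, 2.2 and 6). A participant can therefore be lost under 7.2 while the primary outcome is still being observed. Section 4.3 has a data rule for hospitalization, but no section has one for loss, and none says whether a replaced participant counts in the adherence denominator.

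**2. The plan's own figures.** Section 6 gives 20 completers and up to 40 enrolled, with no drop-out rate, power or precision target, so the 20 cannot be reproduced. The allowance implied by the two figures is d in 20/(1 − d) = 40, so d = 50%. Up to 40 − 20 = 20 enrolled participants could fall outside the completers. That total covers drop-out and exclusion of every kind, not only failed contact.

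**3. How far the denominator can move the result.** Assume that each participant is scored adherent or not, and that 14 of 20 retained participants are adherent: 14/20 = 70%, exact (Clopper-Pearson) 95% interval 45.7% to 88.1%. With L participants lost and replaced, the all-enrolled proportion lies between 14/(20 + L), if none of the lost is adherent, and (14 + L)/(20 + L), if all are.

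| Lost (assumed) | Lowest | Highest |
|---|---|---|
| 2 | 14/22 = 63.6% | 16/22 = 72.7% |
| 5 | 14/25 = 56.0% | 19/25 = 76.0% |
| 10 | 14/30 = 46.7% | 24/30 = 80.0% |
| 20 (enrolment cap) | 14/40 = 35.0% | 34/40 = 85.0% |

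Sampling error with 20 participants is already wide, and the first three ranges fall inside the exact interval. The uncertainty about the denominator is additional to that. It could be removed for any lost participant whose mat is still transmitting.

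**4. Direction.** Let p be true adherence, and let a and b be the loss rates in adherent and non-adherent participants. Expected adherence among those retained is p(1 − a)/[p(1 − a) + (1 − p)(1 − b)]. With p = 60% (all values assumed):

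- a = 10%, b = 10%: 0.54/(0.54 + 0.36) = 60.0%
- a = 10%, b = 30%: 0.54/(0.54 + 0.28) = 65.9%
- a = 10%, b = 50%: 0.54/(0.54 + 0.20) = 73.0%
- a = 30%, b = 10%: 0.42/(0.42 + 0.36) = 53.8%

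The shift can go either way, and it is zero when loss is unrelated to adherence.

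**The case against.** The strongest reply is that contact matters in this study. Ulcers and health care use are learned from monthly calls, and temperature alerts are handled by speaking to the participant. Someone who cannot be reached is a real loss for those purposes. Enrolling one more person also does not remove the first, and the count of losses is listed separately from the adherence definition. On this view the plan has only left an analysis set unstated.

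Much of this stands. Contact is a sensible criterion for the call-based outcomes. But the plan uses it as the only criterion for the whole study, ties it to replacement and counts its target in completers. Together these can select the sample on which adherence is reported.

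Several stronger readings are tempting, and the documents do not support them:

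- **That lost participants' mat data are discarded.** No section says so. Their place in the analysis is simply not stated.
- **That one unanswered monthly call makes a participant lost.** Being impossible to reach is not the same as missing one call. The plan also has other contact, after missed mat use and after temperature elevations. The number lost this way cannot be estimated from the documents.
- **That the rule also fails for someone who takes calls but has stopped using the mat.** In an adherence study that person is an observed non-adherer, correctly counted as followed.
- **That adherence will be overstated.** This needs people who are hard to reach to use the mat less, which is an assumption. Losing people who still use it would tend to lower the estimate.
- **That medical records could replace the calls.** The documents use the EMR to identify patients and to extract baseline demographics. They do not establish it as a source for follow-up visits.

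**Conclusion.** The concern holds in a limited form. Followed as written, Section 7.2 allows a participant who is still transmitting to be declared lost and replaced, and nothing in Section 6 keeps that person in the primary denominator. The adherence estimate may therefore describe a selected group of completers.

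The size depends on how many are lost and how they used the mat, and the documents give neither. With an assumed 14 of 20 adherent and 5 lost, the all-enrolled result could be anywhere from 56% to 76%, against 70% among those retained. These bounds apply to participants lost for any reason. Those who are out of contact but still transmitting are a subset of unknown size. The documents also do not say whether the mat stays active once a participant is declared lost, so complete adherence data in such a person are possible but not certain.

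**What to change.** State the following in Sections 7.2 and 6:

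1. Failed contact alone does not end follow-up for the primary outcome.
2. Every enrolled participant stays in the primary adherence denominator and is scored on mat transmissions, whether or not an additional participant is enrolled.
3. Days without a transmission count as non-use, with three exceptions: periods when mat use was stopped on study instruction (Section 1.2 C), time after censoring at hospital admission (Section 4.3), and time after withdrawal of consent to data collection.
4. Loss to contact is reported separately and applies only to the secondary outcomes collected by telephone.

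The cost is a few sentences and a little more analysis work. No new visits or measurements are needed, because the transmissions are already part of the study. The device company would need to keep supplying mat records for participants who are out of contact with study staff. The downside to accept is that the reported adherence may be less favourable than a figure for completers only.
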